2.9 Patient-reported outcomes (PROs)

The FAS will be used for analysing PRO data unless otherwise specified. The summary tables will be presented for 'Responders', 'Non-responders' and 'All subjects'. Listings will be provided. Box plots showing parameter values over time will be displayed, as applicable. Boxplots will display boxes (25th – 75th percentiles) and median (line) as well as joint mean (dot) values. Whiskers extend to the 10th – 90th percentiles with any values outside the whiskers not being displayed.

2.9.1 FACIT-Fatigue and FACT-TH18 (includes FACT-G)

Functional assessment of chronic illness therapy (FACIT)-Fatigue, functional assessment of cancer therapy-thrombocytopenia 18 (FACT-TH18) and functional assessment of cancer therapy-general (FACT-G) responses will be generated in accordance with the respective scoring manual. Descriptive statistics will be used to summarise the actual subtotal/total score and absolute change from baseline to each visit assessment. Patients with an evaluable baseline score and at least one evaluable post baseline subtotal/total score during the on-treatment period will be included in the change from baseline analyses.

Missing responses for items in a scale will be handled based on the respective instrument manual. All PRO analyses will include data as imputed according to the scoring manual. No imputation will be applied if the total or subscale scores are missing at a visit.

FACIT-Fatigue

There are 13 items. Negatively worded items are reverse scored prior to summing. Add the scores together, multiply by 13 and then divide by the number of items answered. A total score of <30 indicates severe fatigue. The higher the total score the better the quality of life. Total score can vary from 0 to 52.

In cases some answers are missing, a total score is prorated from the score of the answered items, so long as more than 50% of the items (i.e., at least 7 of 13) were answered.

```
FAT_N = N(OF HI7 HI12 AN1-AN5 AN7 AN8 AN12 AN14-AN16);  
IF (FAT_N/13 > 0.50) THEN Fatigue = SUM(OF HI7 HI12 AN1-AN5 AN7 AN8 AN12  
AN14-AN16)*13/(FAT_N);
```

Further details on the **FACIT-Fatigue** scoring is provided in [Appendix 6.4](#) and at:

<http://www.facit.org/FACITOrg/Questionnaires>

http://www.physio-pedia.com/Functional_Assessment_of_Chronic_Illness_Therapy

FACT-TH18 and FACT-G

There are 27-items divided into 4 domains in the FACT-G part, Physical Well-Being (PWB), Social/Family Well-Being (SWB), Emotional Well-Being (EWB), Functional Well-Being (FWB). Calculate the total scores for each subscale and overall in a similar way as for the FACIT-Fatigue, i.e. after reversing the scoring of negatively worded items (so that a higher score always indicated a favorable response), item responses are summed.

In cases where some answers may be missing, a total score is prorated from the score of the answered items, so long as more than 50% of the items were answered. E.g. for PWB, where $PWB_N = N(OF GP1-GP7)$ i.e. number of items not missing in GP1 to GP7

```
IF (PWB_N/7 > 0.50) THEN PWB = SUM(OF GP1-GP7)*7/(PWB_N);
```

[figure not shown]
Note that a total score should only be calculated if ALL of the component subscales have valid scores.

[figure not shown]
Summary of the total scores:

- FACT-G total score: PWB score + SWB score + EWB score + FWB score
- FACT-Th total score: PWB score + SWB score + EWB score + FWB score + ThS score
i.e. FACT-Th total score = FACT-G total score + Th subscale score
- FACT-Th Trial Outcome Index (TOI): PWB score + FWB score + ThS score

Further details on **FACT-TH18** and **FACT-G** scoring is provided in [Appendix 6.4](#) and at:

<https://www.rtog.org/LinkClick.aspx?fileticket=bAZw9mE3jlQ%3D&tabid=118>

2.11 Interim analysis

There are 2 planned reporting events, each with a CSR:

- Primary analysis (6 months)
- Final analysis (24 months)

3 Sample size calculation

50 patients will be enrolled in the study.

With 50 patients criteria

- a: observed overall hematologic response rate (ORR) \geq “clinically meaningful” threshold (30%) and
- b: probability of true overall hematologic response rate “not being clinically meaningful (response \leq 20%)” is less than 10%

will be met if at least 15 responders out of 50 patients treated with combination therapy, eltrombopag+cyclosporine are observed by 6 months.

With 54 patients the criteria will be met if at least 17 responders out of 54 patients are observed.

Table 3-1 Table showing observed response rate and its posterior distribution using a Beta-binomial model

Sample size	No. of responders	Observed response rate (%)	Probability of ‘not being clinically meaningful (response rate \leq 20%)’
N=50	13	26.0	0.1693
	14	28.0	0.0992
	15	30.0	0.0538
	16	32.0	0.0269
	17	34.0	0.0125
	18	36.0	0.0059
N=54	14	25.9	0.1618
	15	27.8	0.0961
	16	29.6	0.0530
	17	31.5	0.0272
	18	33.3	0.0130
	19	35.2	0.0065

For example, if 15 responders out of 50 patients are observed, the observed ORR will be 30% and the posterior probability that $\theta \leq 20\%$ is 0.0538. The latter is found using the posterior distribution $\theta|Y \sim \text{Beta}(0.25 + 15, 1 + 50 - 15)$. In R this would be calculated as `pbeta(0.2, 15.25, 36)`.

The operating characteristics of the design are presented in the table below. This table shows the probability of a positive conclusion (i.e. success criteria met at the end of the study) under different underlying true response rates. When the effect of the combination therapy is not clinically meaningful (true response rate \leq 20%), the probability of a positive conclusion is $<10\%$ (false success rate). The probability of success is $>94\%$ when the true response rate by 6 months is 40%.

Table 3-2 Operating characteristics of the study design

Sample size	True response rate (%)	Probability of positive conclusion
N=50	10	0.0001
	20	0.0607
	30	0.5532
	40	0.9460
	50	0.9987
N=54	10	0.0000
	20	0.0310
	30	0.4567
	40	0.9235
	50	0.9981

From [Table 3-1](#) it is known that at least 15 responders need to be observed in 50 patients for study success. The operating characteristics in [Table 3-2](#) are now the probabilities under a given assumed true ORR to observe ≥ 15 responders. For example, if the assumed true response rate is 40%, this probability is 0.9460 and is found by using the cumulative binomial distribution function. In R, this would be calculated as $1 - \text{pbinom}(14, 50, 0.4)$.

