6.5	FACT-TH18 and FACT-G scoring guideline	41

List of abbreviations

AE	adverse event
AESI	adverse events of special interest
ALP	alkaline phosphatase
ALT	alanine aminotransferase
ANC	absolute neutrophil count
AST	aspartate aminotransferase
ATC	anatomical therapeutic classification
ATG	anti-thymocyte globulin
AUC	area under the curve
BM	bone marrow
CM	concomitant medication
CR	complete response
CRS	case retrieval sheet
CSR	clinical study report
CTCAE	common terminology criteria for adverse events
CV	coefficient of variation
DHP	data handling plan
DI	dose intensity
DNA	deoxyribonucleic acid
EC/ECG	electrocardiogram
ECOG	eastern cooperative oncology group
eCRF	electronic case report form
EOT	end of treatment
FACIT	functional assessment of chronic illness therapy
FAS	full analysis set
FPFV	first patient first visit
GPS	global programming & statistical environment
HLGT	high level group term
HLT	high level term
HR	heart rate
IST	immunosuppressive therapy
LB	laboratory
LLOQ	lower limit of quantification
LPLV	last patient last visit
MedDRA	medical dictionary for drug regulatory affairs
NCDS	Novartis clinical data standards
NGS	next generation sequencing
NMQ	Novartis MedDRA queries
ORR	overall response rate
PA	protocol amendment
PAS	pharmacokinetic analysis set
PDI	planned dose intensity
PDS	programming data specifications
PK	pharmacokinetics
PNH	paroxysmal nocturnal hemoglobinuria
PPS	per-protocol set

PR	partial response
PRO	patient-reported outcomes
PT	preferred term
QTcF	QT correction Fridericia
RBC	red blood cells
RDI	relative dose intensity
[REDACTED]	[REDACTED]
RT-PCR	reverse transcription polymerase chain reaction
SAA	severe aplastic anemia
SAE	serious adverse event
SAP	statistical analysis plan
sd	standard deviation
SI	international system of units
SMQs	standardized MedDRA queries
SOC	system organ class
TBL	total bilirubin
TFLs	tables, figures, listings
TPO-R	thrombopoietin receptor
ULOQ	upper limit of quantification
VS	vital signs
[REDACTED]	[REDACTED]

1 Introduction

This statistical analysis plan (SAP), describes the analyses for the CETB115E2403 study and is based on protocol v02, dated 26-Feb-2019. Enrollment was completed on 11-May-2020 with fifty four (54) adult patients. The interim database lock for the primary analysis was on 09-Dec-2020.

There are 2 planned reporting events:

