3.1.1 Bayesian calculus for a binary endpoint

For the binary endpoint ORR, let Y be the number of responders in n subjects. The sampling model is binomial

$$Y | \theta \sim \text{Bin}(n, \theta)$$

with true response rate θ . The prior distribution is a Beta distribution

$$\theta \sim \text{Beta}(a, b)$$

In this conjugate setting, the posterior distribution is again a Beta distribution

$$\theta | Y \sim \text{Beta}(a+Y, b+n-Y)$$

Here, the parameters a and b are the a priori number of responders and non-responders, respectively, and $a+b$ is the prior effective sample size.

For this study, the parameters (a, b) of the Beta prior distribution are $a = 0.25$ and $b = 1$. This prior distribution has mean = $a / (a + b) = 0.25 / (0.25 + 1) = 0.2$ assuming a low response rate a priori. Furthermore, the prior effective sample size is small ($a + b = 1.25$).

4 Changes to protocol specified analyses

Supportive efficacy analyses were added as specified in [Section 2.5.2](#).

Not all laboratory and liver event data will be listed, listings for key biochemistry, hematology and hepatic parameters will be provided.

Sample size characteristics were added based on the enrollment of 54 patients.

Age categories is changed to <60, >=60. Additional subgroups analysis by age, ethnicity and/or responder status were added for demographic characteristics, overall hematological response, transfusion information and relevant AEs.

Boxplots displaying parameter values over time for the patient-reported outcomes were added.

5 References

1. Brookmeyer R and Crowley J (1982). A Confidence Interval for the Median Survival Time. *Biometrics*, 38, 29 - 41.
2. Clopper CJ and Pearson ES (1934). The use of confidence or fiducial limits illustrated in the case of the binomial. *Biometrical*, 26, 404-413.
3. Collet D (1994). Modelling survival data in medical research. London, Chapman & Hall.
[REDACTED]
4. [REDACTED]
5. Neuenschwander B, Branson M and Gsponer T (2008). Critical aspects of the Bayesian approach to Phase I cancer trials. *Statistics in Medicine*, 27, 2420-2439.
6. Oncology guideline for safety analysis, v1.0, dated 09-Jun-2016
7. Spiegelhalter DJ, Abrams KR and Myles JP (2004). Bayesian Approaches to Clinical Trials and Health-care Evaluation. Chichester, Wiley.

6 Appendix 1

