6.3 Statistical models

6.3.1 Primary analysis

Calculation of posterior probability

The efficacy criteria for this study are:

1. Observed overall hematologic response rate \geq “clinically meaningful” threshold (30%)
2. Probability of true overall hematologic response rate “not being clinically meaningful (response \leq 20%)” is less than 10%

Let p denote the proportion of patients who achieves overall hematologic response by 6 months and follow a beta prior distribution Beta [a, b], where $a > 0$, $b > 0$. Let y out of n patients achieve overall hematologic response by 6 months. Therefore, the posterior distribution of p is Beta[a+y, b+n-y] [Spiegelhalter et al. 2004].

A minimally informative unimodal Beta prior [Neuenschwander et al. 2008] Beta [0.25, 1] will be used. The parameters were chosen so that the posterior probability of the true response rate $\leq 20\%$ (considered not clinically meaningful) is equal to 0.0538.

The efficacy criteria will be assessed based on the actual number of patients enrolled in the study. For example, if the total number of patients is 50, the efficacy criteria requires that at least 15 patients achieve overall hematologic response by 6 months. In that case, the posterior

distribution is Beta[0.25+15, 1+50-15] i.e. Beta[15.25, 36] and the probability of success is >90% when the true responder rate is 40%.

Confidence interval for response rate

Responses will be summarised in terms of percentage rates with $100(1 - \alpha)\%$ confidence interval using exact binomial confidence interval (implemented using SAS procedure FREQ with EXACT statement for one-way table [\[Clopper and Pearson 1934\]](#)).

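### SAP Section 3 states a success probability above 94% at a true 40% response rate, but for the 54 patients enrolled it is 92.3%; two Table 3-1 posterior probabilities also do not reproduce

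*SAP*

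**What the plan says.** Protocol Section 10.8 plans 50 patients and reports operating characteristics for that size alone, including a success probability above 94% at a true response rate of 40%.

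The SAP repeats this in Section 3 with no sample size attached: "The probability of success is $>94\%$ when the true response rate by 6 months is 40" (per cent). By then the basis had changed:

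- SAP Section 1: "Enrollment was completed on 11-May-2020 with fifty four (54) adult patients".
- SAP Section 3: "With 54 patients the criteria will be met if at least 17 responders out of 54 patients are observed".
- SAP Section 4: "Sample size characteristics were added based on the enrollment of 54 patients".
- SAP Section 6.3.1: "The efficacy criteria will be assessed based on the actual number of patients enrolled in the study".

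Table 3-2, directly below the 94% statement, gives 0.9460 for N=50 and 0.9235 for N=54 at a true rate of 40%. The paragraph after the table starts from the fact that "at least 15 responders need to be observed in 50 patients for study success" and then describes the entries as probabilities of 15 or more responders.

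Table 3-1 gives the posterior probability that the true rate is 20% or lower, under a Beta(0.25, 1) prior. Its last row in each block reads 0.0059 (18/50) and 0.0065 (19/54).

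**The concern.** The 94% statement is true of the planned design and false of the design on which the criteria are judged, and the text gives no cue to that. The statement just before it, that false success stays below 10%, also names no sample size and holds for both, so a reader would naturally take the next one to hold for both as well. The direction is not one a reader would guess either: four more patients lowered the probability of success.

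The explanation of Table 3-2 has the same gap. Anyone who applies the 15-responder rule to the N=54 rows will not reproduce them.

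The two Table 3-1 cells are a separate matter. They disagree with the formula that the SAP gives for computing them.

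At stake is the accuracy of quoted figures. Someone citing the statement would overstate the analysed design's success probability by about 2 percentage points.

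**Working it through.** **Inputs.** Success needs (a) an observed rate of at least 30% and (b) a posterior probability below 10% that the true rate is 20% or lower (SAP Sections 3 and 6.3.1). The prior is Beta(0.25, 1) (SAP Section 3.1.1). The sample sizes are 50 planned and 54 enrolled. All 54 are assumed to have received study treatment, so that the full analysis set is 54.

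**Formulas.** With y responders in n patients, the posterior probability is the Beta(0.25 + y, 1 + n − y) distribution function at 0.2. The probability of success at true rate p is P(X ≥ r) for X ~ Bin(n, p), where r is the smallest count that meets (a) and (b).

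**Success bars.**

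- N=50: 15/50 = 30.0% with posterior 0.0538. Both criteria are met, so r = 15.
- N=54: 16/54 = 29.6% with posterior 0.0530. This meets (b) but fails (a). 17/54 = 31.5% with posterior 0.0272 meets both, so r = 17.

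Both bars agree with the SAP. Criterion (a) and whole-number rounding explain the lower success probability: the bar rises from 30.0% to 31.5%.

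**Probability of success.** The N=50 column reproduces the protocol and the SAP; the N=54 column reproduces the SAP.

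| True rate | N=50, r=15 | N=54, r=17 |
|---|---|---|
| 10% | 0.0001 | 0.0000 |
| 20% | 0.0607 | 0.0310 |
| 30% | 0.5532 | 0.4567 |
| 40% | 0.9460 | 0.9235 |
| 50% | 0.9987 | 0.9981 |

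All ten entries match Table 3-2 to four decimals. At 40% the unrounded values are 0.94604 and 0.92348, a difference of 0.0226. The chance of missing the bar rises from 5.4% to 7.7%. Solving P(X ≥ 17 | 54, p) = 0.94 gives p = 0.4085, so a true rate of about 40.9% is needed before 94% is reached with 17/54.

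**The explanation of Table 3-2.** Using 15 or more responders with N=54 gives 0.9778 at 40% and 0.1068 at 20%. The table prints 0.9235 and 0.0310. The table is right for r = 17; the general description fits only the N=50 rows. The 0.1068 would also exceed the 10% false-success limit that the SAP states.

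**Table 3-1.**

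| n | y | Printed | Recomputed |
|---|---|---|---|
| 50 | 13 | 0.1693 | 0.1693 |
| 50 | 14 | 0.0992 | 0.0992 |
| 50 | 15 | 0.0538 | 0.0538 |
| 50 | 16 | 0.0269 | 0.0269 |
| 50 | 17 | 0.0125 | 0.0125 |
| 50 | 18 | **0.0059** | **0.0053** |
| 54 | 14 | 0.1618 | 0.1618 |
| 54 | 15 | 0.0961 | 0.0961 |
| 54 | 16 | 0.0530 | 0.0530 |
| 54 | 17 | 0.0272 | 0.0272 |
| 54 | 18 | 0.0130 | 0.0130 |
| 54 | 19 | **0.0065** | **0.0057** |

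In the SAP's own R notation, pbeta(0.2, 18.25, 33) = 0.005334 and pbeta(0.2, 19.25, 36) = 0.005739. The printed cells are too high by 0.0006 and 0.0008, which rounding cannot explain. Ten of twelve cells match, so the prior and method are not in doubt. Five other priors were tried, (0.2, 0.8), (1/3, 1), (0.5, 0.5), (1, 1) and (0.25, 0.75); all gave values below the printed ones for these two cells.

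**The case against.** The strongest reply is that nothing is hidden. Table 3-2 prints 0.9235 immediately after the statement, and Section 4 declares the 54-patient additions. Section 3 opens with "50 patients will be enrolled in the study", and the worked example at 40% uses N=50 throughout, so a reader is led towards that size. For that size the figure is correct: the statement is unqualified, not miscalculated. The explanation of Table 3-2 also mentions 50 patients just before it gives the 15-responder rule. The primary database lock was in December 2020, and a success probability under an assumed true rate feeds no remaining analysis. The two cells lie above the success bars and far below 10%.

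Much of this stands, and it is why the point is a low-severity one. It does not rescue the statement. Section 6.3.1 ties the assessment to actual enrolment, and the text disagrees with the N=54 row of its own table. The SAP shows elsewhere that it can be explicit: the figure above 90% in Section 6.3.1 is attached to a 50-patient example and needs no change.

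On the cells, the documents do not show whether the cause was typing or calculation, and a misread digit in the text extracted from the PDF cannot be fully excluded for 18/50. It is unlikely for 19/54, where two digits differ. What can be said is that the values do not reproduce.

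**Conclusion.** The concern holds, at low severity. At a true response rate of 40% the probability of success is 94.6% for 50 patients and 92.3% for the 54 enrolled, so the unqualified claim of more than 94% is wrong for the analysed design by about 2 points. False success at a true 20% is 6.1% and 3.1%, both within the stated 10%. The explanation of Table 3-2 covers only half of the table. Two of the twelve Table 3-1 cells are too high, by 0.0006 and 0.0008.

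None of this changes the decision rule, the 15/50 and 17/54 bars or the completed primary analysis. The 92.3% rests on a full analysis set of 54 and on the SAP's stated criteria and binomial model.

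**What to change.** - **SAP Section 3, success probability.** Replace the statement with: *At a true response rate of 40% the probability of success is 94.6% with 50 patients (at least 15 responders) and 92.3% with the 54 patients enrolled (at least 17 responders); the false success rate at 20% is 6.1% and 3.1%.*
- **SAP Section 3, text explaining Table 3-2.** Describe the entries as the probability of at least 15 responders for N=50 and at least 17 for N=54.
- **SAP Table 3-1.** Change 0.0059 to 0.0053 (18/50) and 0.0065 to 0.0057 (19/54), after checking the printed cells against the source file.
- **Final clinical study report.** If it quotes operating characteristics, use the N=54 figures.

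The cost is one sentence, one clause and two table cells. The stated success probability becomes about 2 points less favourable. No re-analysis is needed.

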3.1.1 Bayesian calculus for a binary endpoint

For the binary endpoint ORR, let Y be the number of responders in n subjects. The sampling model is binomial

$$Y | \theta \sim \text{Bin}(n, \theta)$$

with true response rate θ . The prior distribution is a Beta distribution

$$\theta \sim \text{Beta}(a, b)$$

In this conjugate setting, the posterior distribution is again a Beta distribution

$$\theta | Y \sim \text{Beta}(a+Y, b+n-Y)$$

Here, the parameters a and b are the a priori number of responders and non-responders, respectively, and $a+b$ is the prior effective sample size.

For this study, the parameters (a, b) of the Beta prior distribution are $a = 0.25$ and $b = 1$. This prior distribution has mean = $a / (a + b) = 0.25 / (0.25 + 1) = 0.2$ assuming a low response rate a priori. Furthermore, the prior effective sample size is small ($a + b = 1.25$).

4 Changes to protocol specified analyses

Supportive efficacy analyses were added as specified in [Section 2.5.2](#).

Not all laboratory and liver event data will be listed, listings for key biochemistry, hematology and hepatic parameters will be provided.

Sample size characteristics were added based on the enrollment of 54 patients.

Age categories is changed to <60, >=60. Additional subgroups analysis by age, ethnicity and/or responder status were added for demographic characteristics, overall hematological response, transfusion information and relevant AEs.

Boxplots displaying parameter values over time for the patient-reported outcomes were added.

5 References

1. Brookmeyer R and Crowley J (1982). A Confidence Interval for the Median Survival Time. *Biometrics*, 38, 29 - 41.
2. Clopper CJ and Pearson ES (1934). The use of confidence or fiducial limits illustrated in the case of the binomial. *Biometrical*, 26, 404-413.
3. Collet D (1994). Modelling survival data in medical research. London, Chapman & Hall.
[REDACTED]
4. [REDACTED]
5. Neuenschwander B, Branson M and Gsponer T (2008). Critical aspects of the Bayesian approach to Phase I cancer trials. *Statistics in Medicine*, 27, 2420-2439.
6. Oncology guideline for safety analysis, v1.0, dated 09-Jun-2016
7. Spiegelhalter DJ, Abrams KR and Myles JP (2004). Bayesian Approaches to Clinical Trials and Health-care Evaluation. Chichester, Wiley.

6 Appendix 1

6.1 Imputation rules

6.1.1 AE, concomitant medication (CM) and safety assessment date imputation

Table 5-1 Imputation of start dates (AE, CM) and assessments (LB, EG, VS)

Missing Element	Rule
day, month, and year	
• No imputation will be done for completely missing dates
day, month	
• If available year = year of study treatment start date then
◦ If stop date contains a full date and stop date is earlier than study treatment start date then set start date = 01JanYYYY◦ Else set start date = study treatment start date.• If available year > year of study treatment start date then 01JanYYYY• If available year < year of study treatment start date then 01JulYYYY
day	
• If available month and year = month and year of study treatment start date then
◦ If stop date contains a full date and stop date is earlier than study treatment start date then set start date= 01MONYYYY.◦ Else set start date = study treatment start date.• If available month and year > month and year of study treatment start date then 01MONYYYY• If available month and year < month year of study treatment start date then 15MONYYYY

LB: Laboratory, EG: ECG, VS: Vital signs

Table 5-2 Imputation of end dates (AE, CM)

Missing Element	Rule (*=last treatment date plus 30 days not > (death date, cut-off date, withdrawal of consent date))
day, month, and year	
• Completely missing end dates (incl. ongoing events) will be imputed by the end date of the on-treatment period*
day, month	
• If partial end date contains year only, set end date = earliest of 31DecYYYY or end date of the on-treatment period *
day	
• If partial end date contains month and year, set end date = earliest of last day of the month or end date of the on-treatment period*

Any AEs and CMs with partial/missing dates will be displayed as such in the data listings. Any AEs and CMs which are continuing as per data cut-off will be shown as 'ongoing' rather than the end date provided.

